## Procedures

Participants who are eligible for the survey study (Part 1) will be directed to the main survey on REDCap. Survey instruments include: Center for Epidemiological Studies-Depression (CES-D), Yale Food Addiction Scale, Social Phobia Scale (SPS-6), Weight Bias Internalization-Modified (WBIS-M), Perceived Treatment Efficacy, Barriers to Help Seeking Scale (BHSS), Financial Stress Measure, Experience of Racism, Stanford Leisure-Time Activity Categorical Item (L-CAT), as well as individual questionnaire items regarding weight loss history, and effects of COVID-19 on health.

Participants who are eligible for the intervention (Part 2) will be immediately linked to a brief introduction to part 2 of this study at the end of the survey and asked to share their contact information (phone number and email address) if they are interested. Research staff will call participants who are eligible and will review the consent form and answer any questions they have about the study and confirm their interest. The participants will be presented with the full informed consent document and consent to participate via signature provided through a REDCap e-consent. After completing this consent, they will be considered enrolled in the intervention.

Participants who indicate interest in the weight loss program will be informed that they will be sent a second survey in one month. They will be asked if it is ok to use the email address they provide for human subject payment to send them this second survey. This survey will ask them if they have joined a weight loss program in the past month, perceived barriers to joining weight loss programs, and if they are interested in the self-weighing program at that time. If they have not joined a weight loss program

and are interested in the self-weighing program, they will be linked to a brief introduction to part 2 (self-weighing intervention) of this study at the end of the survey and asked to share their contact information. Procedures to consent and enroll them in part 2 will be as described above.

After a participant consents to part 2, they will be sent a standalone questionnaire, called the eating disorder examination questionnaire (EDE-Q). This will be sent to the participant's email address via the REDCap platform.

After Part 1 (first survey) all participants will be directed in REDCap to an invitation to share their weight data from their EHR beginning one year prior to the study until 3 years after the study (Part 2b). Interested participants will be presented with an informed consent document and consent to participate via signature provided through a REDCap e-consent.

## **Intervention**

All intervention elements are delivered remotely. Participants who enroll in the intervention (Part 2) will be mailed a cellular-connected "smart" scale (BodyTrace, Inc). Participants will also receive a study handout with instructions on obtaining an accurate weight (e.g., weigh themselves daily, first thing in the morning, after voiding), suggestions for remembering to self-weigh (e.g., placing the scale in a prominent location), and assistance in interpreting changes in weight (e.g., how to spot trends and noting that day-to-day weight fluctuations are normal). Participants will be informed in the consent process that BodyTrace is a third party and data stored there are not regulated by UF.

Every other week, text messages will be sent to the participant's personal cell phones. Messages will be delivered via REDCap/Twilio integration. Messages will differ based on weight change observed and the frequency of scale use over the preceding 2-4 weeks. A library of messages is provided with this submission.

Participants who regularly self-weigh and are not gaining weight will receive messages encouraging them to continue weighing themselves. A message encouraging use of weight management resources will be sent to participants who gain  $\geq 1.5\%$  of their baseline body weight over a 2 or 4 week period, or if a 3% weight gain from baseline is detected. In particular, the first message sent to those with weight gain will ask if they are willing to receive suggestions for weight management. Participants who respond "yes" will be asked to text back how much time per week are they able to spend managing their weight from the choices of <30 minutes or 30 minutes–2 hours. Participants who select <30 minutes will be given information about a popular, freely available online tool for tracking dietary and physical activity (MyFitnessPal). Participants who select 0.5-2 hours will be asked a few additional questions (e.g., preference for in-person vs remote approaches; barriers to weight

loss), then they will be sent information on selected free/low-cost, evidence-based community-based and commercial weight-loss options.

If participants weigh themselves  $\leq 5$  times per week, we will send them tips to increase self-weighing. If this is followed by a period of very infrequent self-weighing (one time per week or less), they will be sent a message suggesting that they may have gained weight and offering weight management resources.

### **Assessments and measures.**

All assessments will be conducted remotely via REDCap. In addition to the Part 1 survey, and the one-month follow-up Part 1 survey (for those who qualify), participants who enroll in the intervention will complete survey assessments at 3 and 12 months, and a portion of participants will be invited to a qualitative interview at 12 months.

#### **Part 1 one-month follow-up survey**

- Study-specific questions about their interest in weight loss programs, and their barriers to joining weight loss programs.

#### **Supplemental Survey/ Part 1**

- **Eating Disorder Examination Questionnaire EDE-Q.**

#### **3- and 12-month surveys**

- **Weight management behaviors.** At 3- and 12-month assessments, we will ask participants if they have engaged in 19 common strategies for weight management since prior assessment using items from the National Health and Nutrition Examination Survey (NHANES). These strategies include eating less food, eating more or less of certain foods, joining a weight-loss program, or using weight-loss medications. We will also ask: (a) for additional details about some of the strategies used (e.g., which weight-loss program) and (b) about the timing of strategy use. This will tell us whether the messages we sent were related to strategy use. We will also ask about their use of food intake tracking apps.
- **Weight management motivation and readiness.** The same questions from baseline/part 1 survey will be asked.
- **Intervention satisfaction.** At 3- and 12-month surveys, participants will rate specific components of the intervention on a seven-point Likert scale, and will be asked to explain their responses. These components will include: (1) helpfulness of self-weighing instructions provided at study onset, (2) ease-of-use of the scale and reasons for any difficulties, (3) helpfulness of message content, (4) frequency of text messages, (5) overall satisfaction with the program, including the things they did or did not like, (6) likelihood of

recommending the program to others and the reasons why, (7) satisfaction with text messages that offered weight-management resources.

- EDEQ
- CESD
- WBIS-M
- COVID-19 health questions

**Self-weighing data from BodyTrace scale.** Self-weighing frequency and weights from self-weighing throughout the 12 month study will be obtained from BodyTrace via an API.

**Qualitative interviews.** At 12 months, we will conduct interviews with 20 participants to better understand their experience of the intervention. Interviews will be conducted over HIPAA-compliant Zoom, with video if participants are willing and able, or otherwise with audio only. The interviews will cover the survey topics (e.g., message content) in greater depth. See interview guide in myIRB.

**Body weight from EHR.** We will extract all clinical body weight data from the EHR of participants from a period beginning one year prior to the study until 3 years after the study.

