The efficacy of self-weighing interventions to prevent weight gain has been supported both by self-regulatory theory and existing empirical research. However, what has not yet been investigated is the effect of a low-burden self-weighing intervention on preventing weight gain in adults with obesity or overweight, and particularly among those who decline behavioral weight-loss treatments. Thus, the current application proposes a pilot study to investigate the feasibility and acceptability of a self-weighing + text messaging intervention. In the proposed intervention, participants will be asked to weigh themselves daily using a “smart” scale that transmits weight measurements directly to the study team via a cellular network. In addition to receiving text messages every other week which provide feedback and encourage continued self-weighing, participants whose weight gain passes a specific threshold will receive an additional, tailored text message. This text message will encourage the use of low-cost evidence-based weight-management resources (e.g., online dietary trackers). Messages encouraging use of resources may be particularly impactful given that they will come at a time when participants may be more willing to consider using resources to manage their weight (i.e., due to recent weight gain). Further, evidence supports the importance of responding quickly to small weight gains in order to prevent larger gains over time. Participants in this intervention who self-weigh infrequently will receive tailored messages aiming to engage them in more frequent self-weighing or in using weight management resources. This intervention approach has high potential for implementation within health care systems given its low complexity and potential for low cost. Further, our preliminary data demonstrate that many adults who decline traditional weight-loss treatments are willing to enroll in this sort of low-burden intervention.

A large clinical trial is needed to test the effectiveness of the proposed intervention. However, prior to that, we need data on feasibility and acceptability of the intervention and trial design, particularly given that individuals declining weight loss treatments have rarely been studied.

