## 5. Specific Aims:

**Aim 1:** Identify predictors of willingness to engage in a weight loss intervention and a weight gain prevention intervention.

**Aim 2:** Determine the feasibility of the trial and acceptability of the intervention. We will examine the following feasibility/acceptability outcomes: intervention enrollment, intervention satisfaction, and whether adequate weight data can be extracted from participants' EHR.

**Aim 3:** Evaluate whether the intervention can promote regular self-weighing and use of evidence-based weight-management resources.

**Overview:** This study has two parts. Part 1 is a 15–20-minute survey, which participants are paid \$10 for completing. Some participants will be offered a second survey one month later, which also pays \$10. Part 2 is a 12-month intervention that involves participants being sent a smart scale, asked to weigh themselves daily, and being sent text messages every other week with feedback on their weight and suggestions for weight management. Part 2 also involves obtaining weight from EHR for 3 years after enrollment. Part 2 participants are paid \$10 for each of two online assessments and \$20 for a qualitative interview, for a total possibility of \$40. Only a portion of participants who complete the first (survey) part of this study will be invited to the second (intervention) part. Participants from Part 1 will be asked if they agree to allow us to obtain weight data from their EHR for a period of four years and will be given an option to complete REDCap e-consent for this.

**Participants, recruitment, and enrollment.** We will recruit UF medical patients aged 18–70 years whose EHR records indicate either obesity ( $BMI \geq 30 \text{ kg/m}^2$ ) or overweight ( $BMI \geq 25 \text{ kg/m}^2$ ) accompanied by a weight-related comorbidity.

We aim to obtain a sample size of 40 participants for part 2 of this study (intervention). We will cease recruiting for part 1 (survey) when we reach that goal. Thus, we are not able to know our total sample size for the entire study in advance, though we estimate that it will be 200.

We will recruit via two approaches:

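### Strategy and app use has no listed baseline, so Aim 3 may count continuing users as initiators, and the surveys can show only a temporal association with the messages

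*Combined protocol and SAP*

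**What the plan says.** Aim 3 (Specific Aims) is to "Evaluate whether the intervention can promote regular self-weighing and use of evidence-based weight-management resources".

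Under the heading for the 3- and 12-month surveys: "At 3- and 12-month assessments, we will ask participants if they have engaged in 19 common strategies for weight management since prior assessment". The items come from NHANES. Participants are also asked for details of some strategies, such as which program they joined, "about the timing of strategy use", and about food-tracking apps. The conclusion drawn is: "This will tell us whether the messages we sent were related to strategy use".

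The Part 1 instruments (Procedures) do not include the 19 items. The nearest content is "as well as individual questionnaire items regarding weight loss history, and effects of COVID-19 on health".

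In the Intervention section, weight-management resources are offered after a gain of at least 1.5% of baseline weight over 2 or 4 weeks, after a 3% gain from baseline, or after a spell of weighing once a week or less. The Background expects these messages to arrive "at a time when participants may be more willing to consider using resources to manage their weight (i.e., due to recent weight gain".

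The Data analyses section will describe willingness to learn about resources, starting to use them and continuing to use them, in the subset to whom they were offered. It presents this as potential for effectiveness. It specifies no analysis that links message dates to the timing of strategy use.

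**The concern.** Starting to use a resource means something only against what the person was doing before. Someone who was already logging meals in an app at enrollment and still does so at month 3 would answer the survey in the same way as someone who began after a text. Without the same questions at baseline, the only safeguard is a recalled start date, and recall reaches back about 9 months at the second survey.

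The second difficulty is what triggers the offers. The resource messages go out because of the participant's own weight or weighing behavior, and the protocol itself says that recent gain may make people readier to act. A strategy begun after a message is what one would see if the message worked, and also what one would see if the gain alone prompted the person. One arm cannot tell these apart.

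The results are meant to inform a larger randomized trial. An inflated initiation figure, or a temporal pattern read as a response to messages, would carry into that trial's design.

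**Working it through.** The protocol gives no figure for expected strategy use, so there is nothing to reproduce. The check sets the sections side by side and sizes each problem under stated assumptions.

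**1. Is there a baseline?**
- The strategy items and the app question are listed only at 3 and 12 months.
- The adjacent item on motivation and readiness is said to repeat the baseline questions. The strategy item carries no such statement.
- Part 1 has weight-loss-history items of unspecified content.
- The exclusion criteria remove people now in comprehensive behavioral treatment or a lifestyle study. They do not remove people who diet on their own or use an app.

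**2. How much could prior use inflate initiation?** Let c be the share of those offered resources who already used one, and p the true start rate among the rest. If every prior user is counted:
- true initiation = (1 − c)p
- apparent initiation = c + (1 − c)p
- excess = c

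With p = 20% (assumed):

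| c (assumed) | True | Apparent |
|---|---|---|
| 10% | 18% | 28% |
| 20% | 16% | 36% |
| 30% | 14% | 44% |

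These are upper limits, because recalled start dates would remove some prior users.

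**3. Is background use likely?** The section on discomforts and risks says that more than half of adults with obesity try to lose weight by themselves in a given year. Taking 50% and a constant rate, the share making an attempt is 1 − 0.5^(3/12) = 15.9% over 3 months and 1 − 0.5^(9/12) = 40.5% over 9 months, with no messages at all. The trial population is not identical, so this is only an order of magnitude.

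**4. Recall windows.** Asking about the time since the prior assessment gives about 3 months at month 3 and 12 − 3 = 9 months at month 12. With a constant monthly start rate h and no message effect, reported use is 1 − (1 − h)^3 against 1 − (1 − h)^9:
- h = 2%: 5.9% against 16.6%
- h = 5%: 14.3% against 37.0%
- h = 10%: 27.1% against 61.3%

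The rates are assumed and the formula models new starts only. The figures matter only if month 3 and month 12 are compared.

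**5. Confounding by the trigger.** Suppose messages do nothing, the start rate is b without gain, and gain multiplies it by r. Because gain triggers the message, the apparent message ratio is rb/b = r. A simulation with b of 3% or 5% and gain in 10% or 20% of periods returned 1.48 to 1.57 for r = 1.5, 1.98 to 2.05 for r = 2, and 2.99 to 3.14 for r = 3. The whole apparent effect comes from the gain.

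**6. Chance proximity.** Texts go out every 14 days, about 52/2 = 26 in a year. While they continue, any strategy start falls within 14 days after some text, so matching must be limited to resource offers. Even then, with an assumed 4-week window, 1, 3 or 6 non-overlapping offers cover 4/52 = 7.7%, 12/52 = 23.1% or 24/52 = 46.2% of the year.

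**The case against.** The sentence says related, not caused. It rests on the detail and timing questions just before it, and these do allow a named program or app and its start date to be set against the resource that was sent. That is a real, if recall-limited, description. Aim 3 also does not depend on the 19 items alone: willingness is seen in text replies, and the Data analyses section speaks of potential effectiveness in a 40-person pilot and leaves effectiveness to a later randomized trial. Use of comprehensive programs is largely screened out at entry, and the weight-loss-history items may hold some baseline information.

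Most of this stands. A reader might infer that the sentence and Aim 3 cannot be supported at all. The documents do not bear that out, since an association can be described and the resource measures can be tabulated without a baseline. A reader might also infer that a rise from month 3 to month 12 will be misread as a growing response, but no such contrast is planned. Habits such as eating less may also be reported in both windows, so the percentages in step 4 would not carry through as computed.

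What the objection does not answer is that self-directed strategies and apps are neither screened out nor listed at baseline, so new use is not reliably separated from continuing use. Nor does it justify the confidence of the sentence, given the triggers and the absence of any stated linking analysis.

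**Conclusion.** The point holds in a limited form. With no listed baseline for the 19 items or app use, the planned initiation measure may count continuing users. The overstatement is at most the share of prior users among those offered resources, for example 10 to 30 percentage points if that share is 10% to 30%. That share is an assumption; the protocol gives none. Because offers follow weight gain or very infrequent weighing in a single arm, the surveys can support a temporal association and cannot attribute use to the messages. This limits the wording of the claim and does not make Aim 3 unanswerable as a descriptive pilot aim. The unequal recall windows are a secondary matter, relevant only if the two survey figures are compared. The conclusion assumes that the Part 1 weight-loss-history items, whose content is not shown, do not already cover current use of the same strategies and apps.

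**What to change.** 1. Send the 19 items and the app-use question once at baseline, with the EDE-Q that is already emailed after Part 2 consent, using a past-3-months window. Add the same window at 12 months, so that baseline, month 3 and month 12 cover about equal periods.
2. In the Data analyses section, define initiation for Aim 3 as use of a strategy or resource not reported at baseline. Report it with change from baseline, as description. A strategy dropped more than 3 months before baseline and later resumed would count as initiation, and the text should say so.
3. Replace the quoted sentence with, for example: *Reported start times and named programs or apps will be matched descriptively to the dates and content of the messages that offered resources, and the result will be reported as a temporal association, not an effect.*

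A comparison of strategy starts in the 4 weeks before and the 4 weeks after each message may look like a natural next step, but it should not be used. With texts every 2 weeks the windows overlap, and for gain-triggered offers the before-window is the gain period itself.

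The cost is a few minutes of participant time, a small edit to the 12-month survey and a weaker claim. A baseline that is not collected would be very hard to recover later.

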### **Sample size.**

The primary goal of this study is to evaluate feasibility and acceptability of the self-weighing intervention, and the sample size was determined based on standards for achieving that goal. We aim to obtain a sample size of 40 participants for part 2 of this study (intervention). We will cease recruiting for part 1 (survey) when we reach that goal. Thus, we are not able to know our total sample size for the entire study, though we estimate that it will be 200.

### **Data analyses.**

We will conduct logistic regression analyses to examine predictors of willingness to engage in the weight management interventions, among the variables measured in the survey.

For those who enroll in Part II, we will describe quantitative ratings of intervention satisfaction (mean and standard deviation of satisfaction items) and will conduct qualitative content analyses of the qualitative questions about intervention satisfaction.

To evaluate the potential for intervention effectiveness, we will calculate a sample mean and standard deviation for number of days per week that self-weighing occurs across the 12 month intervention and in each quarter of the intervention (to evaluate sustainability of self-weighing). We will evaluate participants' willingness to learn about weight management resources offered by the research team, initiation of use of resources, and sustain use of resources among those participants offered resources. Finally, we will characterize weight change by reporting means, standard deviations, and the portion who gain  $\geq 3\%$  of baseline weight in order to inform planning for our subsequent trial.

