#### *Exclusion criteria*

- Currently enrolled in comprehensive behavioral weight loss treatment or lifestyle-focused research study.
- Has engaged in self-weighing  $\geq 5$  times per week over prior month.
- Pregnant, breastfeeding, or planning to become pregnant in next 6 months.
- Currently undergoing radiation or chemotherapy for cancer.
- History of Congestive Heart Failure or heart attack in past 6 months.

- History of eating disorder.
- Planning to move out of the region in the following 12 months.
- Answer incorrectly on an attention check/ validation survey item.
- Report unwillingness to use data plan for this study.

Participants will be identified as eligible or ineligible for the intervention component (Part 2) based on responses of the survey study (Part 1, including one-month follow-up). The criteria for eligibility (in addition to being eligible to complete the survey) are:

- Respond “No” to question asking if they would like to enroll in a comprehensive weight loss program in the next month. AND
- Respond “yes” to question asking about interest in a self-weighing weight gain prevention intervention.

OR

- On the one-month follow-up Part 1 survey, respond that they have not enrolled in a weight loss program in the prior month, and that they are interested in a self-weighing weight gain prevention program

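### If the 11 or more survey measures for Aim 1 enter one model in about 200 people, Firth-penalised logistic regression would give less biased and more precise odds ratios than maximum likelihood, at almost no cost

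*Combined protocol and SAP*

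**What the plan says.** Aim 1, under Specific Aims, is to "Identify predictors of willingness to engage in a weight loss intervention and a weight gain prevention intervention". The Part 2 eligibility list that follows the exclusion criteria shows that both outcomes are yes/no answers. One is the "question asking if they would like to enroll in a comprehensive weight loss program in the next month"; the other is the "question asking about interest in a self-weighing weight gain prevention intervention".

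The Procedures section names nine instruments for the Part 1 survey, "as well as individual questionnaire items regarding weight loss history, and effects of COVID-19 on health". Counting each of those two item groups once gives 11 measures.

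The whole analysis plan for Aim 1 is one sentence under Data analyses, which promises "logistic regression analyses to examine predictors of willingness to engage in the weight management interventions, among the variables measured in the survey". It does not state the estimator, whether measures enter jointly or one at a time, or any selection or significance rule.

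The Sample size section bases the numbers on feasibility and acceptability. Part 1 recruitment ends once 40 people are in Part 2: "Thus, we are not able to know our total sample size for the entire study, though we estimate that it will be 200".

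**The concern.** Logistic regression is usually fitted by maximum likelihood. With few events per predictor, maximum-likelihood log odds ratios are biased away from zero and are more variable than they need to be. Here at least 11 measures compete for the information in about 200 yes/no answers, and the rarer answer sets the effective size.

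Estimating these odds ratios is the whole of Aim 1. Inflated, noisy estimates could point the later trial towards the wrong patient characteristics. Nothing outside Aim 1 depends on them.

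**Working it through.** **Inputs from the documents.** Part 1 size is about 200 (Sample size). Candidate measures are 9 + 2 = 11 (Procedures). This is a lower bound, because an item group may need several parameters and the 3- and 12-month survey section implies motivation and readiness questions at baseline too.

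**Inputs assumed.** Events means the rarer of the two answers. No willingness rate is given, so I take 14, 40 and 100 of 200. The Background says 80–93% decline weight-loss treatment, so 7–20% accept, or 14–40 per 200. That is treatment uptake, not a rate for either survey question. An even split, 100, is the most favourable case.

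**1. The plan's own figure.** The 200 and the 40 come with no rate, power or significance level, so there is nothing to reproduce. The ratio 40/200 = 20% is the share expected to enter Part 2, not a willingness rate for either question.

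**2. Events per predictor = events / predictors, joint model.**
- 100/11 = 9.1
- 40/11 = 3.6
- 14/11 = 1.3

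**3. Simulation of the joint model.** The settings were n = 200, 11 normal predictors, pairwise correlation 0.3, two true log odds ratios of 0.50 and nine of zero, with 3,000 runs per setting. Five runs at 14 events were excluded for separation or non-convergence.

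| Events | Maximum likelihood: mean (bias) | Firth: mean (bias) | RMSE, maximum likelihood to Firth | Reduction |
|---|---|---|---|---|
| 14 | 0.59 (+19%) | 0.49 (−2%) | 0.48 to 0.37 | 0.11/0.48 = 23% |
| 40 | 0.56 (+11%) | 0.51 (+2%) | 0.26 to 0.23 | 0.03/0.26 = 12% |
| 100 | 0.54 (+8%) | 0.50 (0%) | 0.21 to 0.19 | 0.02/0.21 = 10% |

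A separate run of 800 replicates gave +18%, +11% and +7% for maximum likelihood and −3%, +1% and 0% for Firth, with the same RMSE values. On the odds-ratio scale, a true exp(0.50) = 1.65 becomes exp(0.56) = 1.75 at 40 events and exp(0.59) = 1.80 at 14.

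Bias is a small part of the error: at 40 events, 0.055²/0.263² = 4.4% of mean squared error. Most of Firth's gain is therefore in precision. Its 95% profile-likelihood intervals covered 96%, 94.5% and 94.5% at 14, 40 and 100 events (1,500 runs).

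**4. Sensitivity.**
- Totals of 160 or 240: maximum-likelihood inflation is +14% or +9% at a 20% willing rate, and +9% or +7% at 50%.
- True odds ratio 1.5, correlation 0 or 0.3, with and without three further real predictors (1,500 runs): maximum likelihood +6% to +15% at 40–100 events and +14% to +25% at 14. Firth stayed between −5% and +3% and cut the standard deviation by 7–11% and 19–25% respectively.

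**5. One predictor per model.** Events per predictor are then 14 to 100. Maximum likelihood exceeds Firth by only 2.0–2.5% at 40–100 events.

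**6. Would a shorter list do better?** With five predictors and Firth, RMSE is 0.34, 0.22 and 0.18 if every omitted measure is null, against 0.37, 0.23 and 0.19 for Firth on all 11. If three omitted, correlated measures are real (log odds ratio 0.50), five-predictor Firth is biased by +25% at 40 events and +23% at 100. Firth on all 11 is then at −1% and +1%. RMSE is 0.275 against 0.268, and 0.228 against 0.216.

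**The case against.** The strongest objection is that the plan never commits to what is criticised. It refers to regression analyses in the plural and does not mention maximum likelihood or one joint model. A reader might infer that an ordinary 11-predictor fit is planned, but the documents do not say so. This stands: the bias figures are conditional on joint entry, and with single-predictor models they nearly vanish. It does not remove the point. Joint entry is within the plan's wording, and single-predictor models answer a different question: at correlation 0.3 they gave 0.63–0.66 where the adjusted effect was 0.50.

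A second objection is that the harm is modest. This also stands. In the odds-ratio-1.5 runs, maximum-likelihood 95% intervals still covered about 94–95%, and at 40–100 events the RMSE gain is about 10%. But that gain comes from the same data at almost no cost.

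A reader might also infer that the list should be cut to a handful of predictors. Step 6 does not support this. A short list is less biased only if the omitted measures have no effect, which is what Aim 1 sets out to learn, and it leaves collected measures unexamined.

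**Conclusion.** The point holds, conditionally, as a minor one. If the 11 measures are fitted jointly, Firth removes an inflation of about 7–11% at 40–100 events and 18–19% at 14, and lowers RMSE by about 10% and 23%. If they are fitted singly, the benefit is about 2–3% at 40–100 events, with no harm.

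That Firth does better in the joint model was consistent across all settings tried. The size of the gain is less certain, because event counts, effect sizes and correlations are assumptions.

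Two stronger conclusions are not supported. A reader might infer that Aim 1 will produce false predictors in about 43% of analyses per outcome (1 − 0.95^11 = 43%). That needs all 11 to be tested at 0.05 and declared on the result, and the plan states no such rule. Nor is the study's main purpose at risk: feasibility and acceptability do not rest on these models.

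**What to change.** In the Data analyses section, replace the Aim 1 sentence with a short specification:
- For each of the two willingness outcomes, fit the survey measures jointly in one Firth-penalised logistic model, stating how each item group is coded.
- Report every odds ratio with its profile-likelihood 95% confidence interval.
- Use no data-driven selection of predictors.
- Present Aim 1 as exploratory, so that no predictor is declared on an unadjusted p<0.05.

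The cost is a few sentences and a different standard software routine. Odds ratios will be slightly smaller than under maximum likelihood. No participants or data are added, and no measure is dropped.
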